3. RESEARCH AIMS AND QUESTIONS

The aim of Workstream 2 is to assess the feasibility and acceptability of the SWEET intervention and the future RCT, and identify any changes that are needed prior to the RCT.

Workstream 2 objectives are to:

- identify optimal patient recruitment pathways (sub-study 1);
- explore the acceptability and usefulness of the intervention to patients (sub-study 1);
- explore feasibility of recruiting women to receive the intervention (sub-study 1);
- explore feasibility of delivering the intervention (sub-study 1);
- explore barriers to, and facilitators of, trial implementation, including (i) willingness of staff to recruit women to a RCT; and (ii) willingness of women to be recruited and randomised to a RCT (sub-study 1);
- test processes for collecting self-reported outcome data (sub-study 1);
- assess the feasibility of accessing, and using, community and GP prescribing data to objectively measure adherence to endocrine therapy (sub-study 2);
- identify any necessary refinements to the intervention and plan of evaluation prior to the RCT (sub-study 1 and 2).

4. METHODS

A. SWEET INTERVENTION

The SWEET intervention is described in Appendix 1. In brief, it includes five elements:

- An animation focussing on necessity of taking AET, common concerns that women have about AET and practicalities of taking AET; this will be provided to women prior to the consultation in step (ii);
- (ii) A consultation with a "HT navigator" (SWEET study nurse), tailored to an individual woman's initial experiences of AET, necessity beliefs and concerns either delivered by delegated SWEET study nurse(s) at site, or through Breast Cancer Now as per site agreement
- (iii) A web-app, containing information, tools to support adherence, and signposting to support;
- (iv) A follow-up consultation with the SWEET study nurse (either face to face, by telephone or video-call) to address any emerging concerns and problems;
- (v) Regular, brief, motivational messages delivered by email or text, promoting adherence and encouraging use of the web-app in the event of any questions or problems.

B. METHODOLOGY AND STUDY DESIGN

We will use mixed-methods to explore acceptability and feasibility issues, including:

- (i) Can we identify and recruit potentially eligible patients?
- (ii) Is it feasible to deliver the initial intervention consultation within 8 weeks of recruitment?
- (iii) Are the baseline and follow-up questionnaires acceptable?
- (iv) Do women find the intervention acceptable and useful?

(v) What is the timeliness and quality of primary care prescription encashment data and/or GP prescribing data, and is it possible to use to compute an objective measure of adherence to AET?

Sub-study 1 is a single arm, non-randomised feasibility study to explore the acceptability and feasibility of delivering the SWEET intervention. Recruited women will receive the intervention and will be followed for 7-8 weeks, at which point they will complete a follow-up questionnaire and some will undergo interviews. Interviews will also be conducted with a sample of participating health professionals (n=8-15).

Sub-study 2 is a retrospective cohort study which will test the processes for obtaining prescription encashment data for a small cohort of women with breast cancer initially prescribed AET at hospital/by consultant recommendation (thereby testing, on a small scale, the processes that will require to be followed in the subsequent RCT). The prescribing history for each individual recruited woman will be obtained through linkage of the sub-study 2 cohort to the National Cancer Registration Database (NCRD) and the NHS Business Services Authority (BSA) Primary Care Prescribing Database (PCPD) [55]. This will provide information on timeliness and completeness. Should there be any issues accessing the prescribing dataset (due to changes with PHE) we will access GP prescribing data.

C. STUDY SITES

Substudies 1 and 2 will draw participants from a minimum of three NHS clinical sites (this may increase to five if required to support recruitment). These are expected to include Newcastle-upon-Tyne Hospitals NHS Foundation Trust (NuTH), Oxford University Hospitals NHS Foundation Trust (OUHFT), and Imperial College Hospital Trust (ICHT), London.

D. ELIGIBILITY

Sub-study 1: The target population for the feasibility study (and subsequent RCT) will comprise women with greatest potential to benefit clinically from AET, that is, women with early-stage ER-positive breast cancer who have medium or high risk of recurrence [49]. Risk of recurrence will be defined following Pan et al [56].

Inclusion criteria:

The following patients will be eligible:

- Aged 18+
- Female
- Diagnosis of ER positive invasive breast cancer
- Medium or high risk of recurrence, defined as one of the following
 - o T2 and N0
 - o T2 and N>0
 - o T1 and N>0
 - T1 and N0 and grade 3.
- Within 3 months of first oral AET prescription (tamoxifen or aromatase inhibitor);
- Completed surgery
- Completed chemotherapy (if applicable)
- Can access to the internet and have an email address; and

Are willing to use a support package with a web-based component.

Women on anti-HER2 therapies or ovarian suppression drugs will be eligible provided they fulfil the above criteria, as will women who have had neo-adjuvant ET and women who have had a previous primary breast cancer (as long as they did not have AET to treat that first cancer).

Exclusion Criteria:

The following patients with early-stage ER+ve invasive breast cancer will be ineligible:

- Male
- Have been prescribed adjuvant CDK4/6i (abemaciclib);
- Have cognitive impairment sufficient to preclude participation, as judged by the clinical team:
- Are unable to read and understand English;
- Had previous AET (for another breast cancer);
- Have not had surgery for breast cancer.

Eliciting and addressing women's AET beliefs and concerns, in light of their initial treatment experience, is the bedrock of the intervention, so it is important that women are at a point when they should have initiated AET by the time of their first consultation with the SWEET study nurse. However, they should not be too far beyond the start of treatment at the time of recruitment. Thus, the focus is on recruiting women within 3 months of when they would have been due to start taking AET.

The evidence-base for the SWEET intervention (including the primary research by the SWEET team) comprises research among women with breast cancer. The intervention has been co-developed in partnership with women with breast cancer. Its suitability for men is not known, therefore, men will be excluded.

Sub-study 2: The target population for this sub-study will be women diagnosed with ER-positive invasive breast cancer who have medium or high risk of recurrence [49]. Risk of recurrence will be defined following Pan et al [56].

Inclusion Criteria:

The following patients will be eligible:

- Aged 18+;
- Female
- Diagnosis of ER positive invasive breast cancer
- Medium or high risk of recurrence, defined as one of the following
 - T2 and N0
 - T2 and N>0
 - T1 and N>0
 - T1 and N0 and grade 3.
- Were first prescribed oral AET (tamoxifen or aromatase inhibitor) within the past 9-36 months*
- Have completed surgery;
- Have completed chemotherapy (if applicable);

Women on anti-HER2 therapies, or ovarian suppression drugs, will be eligible provided they fulfil the criteria above, as will women who have had neo-adjuvant ET, and women who have had a previous primary breast cancer (as long as they did not have AET to treat that first cancer).

* This timeframe has been chosen as there is a delay of several months in prescription encashment data being available through the NHS BSA, and for that in turn, to be available through NCRD.

Exclusion Criteria:

The following patients with early-stage ER+ve invasive breast cancer will be ineligible:

- Male
- Have been prescribed adjuvant CDK4/6i (abemaciclib);
- Have cognitive impairment sufficient to preclude participation, as judged by the clinical team;
- Are unable to read and understand English;
- Had previous AET (for another breast cancer);
- Have not had surgery for breast cancer.

E. SAMPLE SIZE

Sub-study 1: The average feasibility study size is 36 [57] but there is little guidance on an appropriate size for our study. We propose to recruit a minimum of 45 eligible women over a period of up to three months (anticipating at least one woman per week per site is achievable, and assuming a minimum of 3 sites recruiting).

We will also conduct interviews with approximately 8-15 health professionals involved in supporting the study at the clinical sites.

Sub-study 2: Based on the logic for sub-study 1, we propose to recruit 45 women to sub-study 2.

F. RECRUITMENT & PROCEDURES

Sub-study 1: Assessment of acceptability & feasibility

Flowchart 1 (Document: *Sub-study 1 Recruitment Pathway* summarises the flow of women through the study.

Identification of eligible women: Two methods will be used to identify potentially eligible women. The second option allows for the identification (and recruitment) of women who received adjuvant chemotherapy (duration approx. 5 months) before starting AET, within the tight timeline for the feasibility study. It is important to test the acceptability of the intervention to this group of women (as well as those who do not have chemotherapy).

Identification Option 1: Potentially eligible women will be identified at an appropriate MDT after their breast cancer surgery. A member of hospital staff will review women's medical records to assess eligibility.

Identification Option 2: Potentially eligible women who underwent adjuvant chemotherapy will be identified from hospital records (e.g. clinician files, medical records or online record systems,

hospital pharmacy records). A member of hospital staff will review women's medical records to assess eligibility.

Recruitment: Two options for recruitment will be used.

Women identified via Identification Option 1: In most instances, we anticipate that eligible women will be approached and provided with the Participant Information Sheet (PIS) at a clinic appointment (Document: *Sub-study 1 Participant Information Sheet*). The initial contact will be made by a research nurse or another member of the hospital team. If not already available, telephone numbers will be obtained for women who are potentially interested in taking part.

At least 24 hours after the receipt of the PIS, a research nurse (or another member of the hospital team) will telephone the woman, answer any questions and, if she wishes to take part, take informed consent (Document: *Sub-study 1 Verbal ICF*). It should be noted that if a woman is happy to be consented immediately, and the study team are satisfied the woman has fully comprehended what is being asked of her, then consent can be taken immediately without a 24 hour wait period. It is acceptable for the patient to complete the baseline questionnaires immediately after informed consent.

Alternatively, women may be sent the PIS in the post ahead of a scheduled clinic appointment. As women approached via this route will have had adequate time to consider their participation, they may be consented at the appointment (Document: *Sub-study 1 ICF*).

The woman will be asked to provide her email address and a phone number. If the woman does not wish to take part, the reason for declining will be recorded on a screening log (Document: *Sub-study 1 Decliners Log*). These reasons will be monitored to identify any issues or common trends that could inform the future design for an RCT.

The woman's appointment with the SWEET study nurse will be confirmed by telephone, email or post by the SWEET Study Nurse. If a site is using the Breast Cancer Now (BCN) support model, the patient details will be shared with the BCN-employed SWEET Study Nurse(s) who will arrange this appointment with the patient. Under both models, the baseline questionnaire and link to the animation will be sent by email or post by the research nurse, dependent on patient preference (see below) (Document: Sub-study 1 Baseline Questionnaire Pack).

For consented women, the site will inform participants' GPs that they are in the study and receiving an intervention to encourage and support hormone therapy adherence (Document – *Sub-study 1 GP letter*).

Women identified via Identification Option 2: A research nurse, or another member of the hospital team, will send a letter of invitation to each woman, signed by her consultant, and enclosing the PIS, ICF and baseline questionnaires (Document: *Sub-study 1 Letter of Invitation*). After a few days, a research nurse or other member of the hospital team will telephone the woman, answer any questions and, if the woman wishes to take part, complete the consent process and prompt the woman to complete the baseline questionnaire as soon as able. The woman will be asked to provide her email address and a phone number in order for her appointment to be arranged. If the woman does not wish to take part, the reason for declining will be recorded, using a standard proforma (Document: *Decliners Log*).

Screening logs: For both methods of identification and recruitment, a research nurse (or another member of the hospital team) will complete screening logs documenting each potentially eligible

patient including whether the relevant clinical data could be found to determine her eligibility (e.g. T, N, grade, anti-HER2 therapy, receipt of chemotherapy), whether she was eligible and, if so, whether she was approached and consented (and, if not, reasons why will be recorded).

Allocating SWEET study nurse appointment & baseline data collection. Once recruited, each woman will be assigned an appointment slot with a SWEET study nurse, this appointment will be confirmed by email or post by the SWEET study nurse. For sites utilising the BCN support model, this will be a BCN nurse. The recruiting site will provide the patient with the baseline questionnaires, a freepost envelope if the woman prefers to complete the questionnaire on paper, and a link to the animation, which she will be asked to view before the SWEET study nurse appointment. Women will be offered the opportunity to reschedule the appointment if the timing does not suit them. Up to two reminders to complete the questionnaire prior to the consultation will be sent if needed (by email in the first instance after 7 days, and by telephone call after 14 days)) .

The baseline questionnaire will include questions on: socio-demographics; lifestyle (e.g. smoking, alcohol consumption, physical activity); AET necessity beliefs (i.e. beliefs about the necessity of taking AET to remain healthy) and AET concerns beliefs (i.e. concerns about the negative effects of taking AET)[58]: whether they have initiated, or intend to initiate, AET; AET adherence (assessed using MARS-5)[69]; and cancer-specific HRQoL (assessed using the FACT-G)[60]; and utility (as measured using the EQ-5D-5L) [61] and an additional health service resource use questionnaire, based on a modified version of the UK Cancer Costs Questionnaire [62]). Baseline and follow-up questionnaires (Document: *Sub-study 1 Baseline Questionnaire Pack* and *Sub-study 1 Follow-up Questionnaire Pack*) were developed with input from the SWEET Patient Advisory Group (PAG)

Relevant medical details for each woman as included on the baseline case report form will be abstracted from medical records by the research nurse or another member of the hospital team. It will be made clear on the PIS and consent form that participation in the study involves agreeing to the individual's medical records being accessed to abstract relevant details.

Delivery of intervention and follow-up: Recruited women will have a consultation with the SWEET study nurse that will last approximately 30 minutes. We intend for these appointments to take place within eight weeks of recruitment and will measure the extent to which this is achieved. The appointment may take place face-to-face or by telephone/videoconferencing, depending on COVID-19 restrictions in place at the time and current practice for follow-up appointments at the relevant site and logistical considerations. Any consultation by SWEET study nurses via the BCN model will always be performed remotely. If a woman does not attend the appointment, she will be sent a second appointment with the option to reschedule again if the date or time does not suit.

Prior to the appointment, the woman will be set-up with an account on the HT&Me web-app using her email address. The woman will be provided with a dummy password which can be changed later if she wishes.

The appointment will be tailored by the SWEET study nurse to the women's beliefs, concerns and AET behaviours using elicitation. The SWEET study nurse will also introduce the woman to the webapp, confirm web-app log-in information and a contact number in event of problems (helpline), and provide the contact number for the local site breast cancer nurses. A sample of consultations will be audio-recorded (approximately one-third, but more may be recorded if necessary) for the purpose of assessing fidelity. It will be made clear on the PIS and consent form that the consultation may be audio-recorded.

The timeline of events following the initial SWEET study nurse appointment will then be as follows:

- Following the appointment: The woman will be sent a letter (by email or post), reiterating her web-app log-in details and enclosing a "how to" guide for the web-app and the helpline number.
- At approximately 10-14 days: The woman will receive the first motivational email/text message. This will prompt her to complete the My Personal Support section of the web-app. The central research team will check whether the woman has accessed the web-app using the web-app analytics data. If she has not, a member of the team will follow-up by phone to encourage and support her to do so.
- At approximately 3 weeks: The woman will receive a second motivational message. The
 content of these may vary across women to enable the central research team to test
 acceptability of different messages. The SWEET study nurse will call her to schedule a
 convenient time for the follow-up consultation.
- At approximately 4 weeks: The follow-up consultation with the SWEET study nurse will take
 place face-to-face or by telephone or video-call. A sample of consultations will be audiorecorded for the purpose of assessing fidelity (approximately one third but more may be
 recorded if necessary). If a woman does not attend the SWEET study nurse appointment, she
 will be sent a second appointment with the option to reschedule if the date or time does not
 suit.
- At approximately 7-8 weeks: The woman will be sent (by email or paper) the follow-up questionnaires. This will assess self-reported adherence and mediator variables to provide an indication of questionnaire acceptability, likely response rate and data completeness (although the timing of administration will be different in the main trial). It will include intervention assessment questions, including ratings of satisfaction with the intervention overall and specific elements such as initial consultation, follow-up consultation, app/website/workbook, email/text message. Women will be asked to describe best bits, where there is room for improvement and, in an open text section, to provide any other comments on the intervention [63]. Participants will also be asked whether they would like ongoing access to the web-app after they have completed their involvement in the feasibility study. To test processes for collecting health economic data, the pack will also include the EQ-5D-5L and a resource use questionnaire. If needed, up to two reminders to complete the questionnaire will be sent (by email, telephone call or post) at approximate 10-day intervals.
- At approximately 8-9 weeks: Semi-structured interviews will be conducted, by a member of the research team (from Newcastle University, Oxford Brookes University or UCL), with a sample of participants (approx. 20-30). These will gauge experiences of recruitment, the intervention (including mode of delivery) and the baseline and follow-up questionnaire, as well as eliciting views on the behaviour change techniques incorporated within the intervention. These interviews will also shed light on why different elements of the website are used/not used.

Interviewees will be sampled for maximum variation based on socio-demographic characteristics and their intervention assessment questionnaire responses. Recruitment will continue until reasonable data saturation, which will be defined as no new issues arising in last three interviews; our experience suggests around 20-30 interviews will be required. A

member of the research team will contact sampled women by telephone to schedule the interview.

Interviews will be face-to-face, by telephone or by video-conferencing according to interviewee preference and relevant COVID-19 guidance in place at the time of the study, and guided by a topic guide (Document: *Sub-study 1 Patient Topic Guide*). They will last approximately 60-90 minutes, or as long as the participant wants. They will be audio-recorded (this will be made clear on the PIS and consent form), transcribed, anonymised, and content analysis [64] conducted to identify key issues relating to recruitment and the intervention.

• Throughout: App/website analytics will also be examined to determine whether women use the web-app and, if so, how often and which elements; it will be made clear on the PIS and consent form that analytic data will be recorded and reviewed.

Factors influencing feasibility: Following each SWEET nurse intervention consultation, the SWEET study nurse will record the date and length of the consultation and, using a checklist informed by TIDieR [65] and intervention BCTs, what was covered. For those interviews which have been audio-recorded, the research team will review the audio-recording of the consultation against the checklist to assess the extent to which the SWEET study nurses can maintain intervention fidelity and quality. The distribution of time between recruitment and the first consultation will be examined as a measure of the feasibility of scheduling these appointments. In the event that a consultation is not delivered to a recruited woman (or the consultation is delivered more than eight weeks post-recruitment), reasons will be documented by the SWEET study nurse.

After three months of patient recruitment at the site, semi-structured interviews with approximately 15-18 key site staff (including, but not limited to, SWEET study nurses, breast cancer consultants, breast cancer nurses and patient navigators) will explore how recruitment and intervention delivery fitted into routine care and any changes that would be required for trial recruitment or intervention delivery to larger numbers of women. Interviews will be face-to-face, by video-conferencing software or telephone, depending on interviewee preference. The SWEET study nurses will also be invited to reflect on experiences of the training package.

Eligible staff will be provided with an Information Sheet (Document: Sub-study 1 HCP Information Sheet) and, after at least 24 hours have passed, contacted to ask whether they would be willing to be interviewed (if staff member is happy to be consented immediately then consent can be taken without 24 hour wait period). Interviews will take place face-to-face, by telephone or videoconference, depending on interviewee preference and COVID-19 restrictions in place at the time. At the outset of the interview, informed consent will be sought (Documents: Sub-study 1 HCP Verbal ICF; Sub-study 1 HCP ICF). The interview will be guided by a topic guide (Document: Sub-study 1 HCP Topic Guide) and will be audio-recorded (this will be made clear on the information sheet and consent form), transcribed, anonymised, and subject to content analysis [85] to identify potential barriers to delivering the intervention and the RCT. Interviews with SWEET study nurses will last approximately 60 minutes; those with other health care professionals are likely to last 30-40 minutes. Interviews will be conducted by a member of the research team from Newcastle University, Oxford Brookes University or UCL.

Optimising the intervention: The assessments of feasibility and acceptability are likely to identify potential changes that, if implemented, could improve the intervention, the manual and training package and planned trial procedures, including assessment of outcomes. Those changes which are

feasible (i.e. possible within the specification of the intervention and context) and congruent with the evidence-base will be implemented, thus optimising the intervention and future RCT.

Participant remuneration: Women who take part in interviews will be offered a £30 voucher as a thank you for their time and to cover any expenses associated with the interview.

Sub-study 2: Testing processes for obtaining prescription encashment data for individual women

The primary outcome for the main RCT will be poor adherence to AET. This will be determined for each woman using, as recommended as best practice [66], a combination of an objective measure (prescription encashment records) and a subjective measure (self-report using the MARS-5) [59]. Although considered a good measure of adherence, encashment slightly overestimates adherence as people may collect medication but not use it. Self-report is highly specific for non-adherence [67] and its use will reduce misclassification in adherence measured using encashment data. Therefore, combining encashment data and self-report at the level of the individual woman will allow us to more correctly classify women.

The purpose of sub-study 2 is to test the process for obtaining prescription encashment data for individual recruited women (thereby testing, in miniature, the processes required in the RCT).

Identification of eligible women: Potentially-eligible women will be identified from hospital records (e.g. clinician's files, hospital systems, medical records, hospital pharmacy records), based on a first prescription for oral AET (Tamoxifen or aromatase inhibitor) in the relevant time window. A member of hospital staff will review women's medical records to assess eligibility.

Recruitment: Different options for recruitment will be available depending on what works best of the individual site.

Option 1: A research nurse, or another member of the hospital team, will send a letter of invitation to each woman signed by her consultant (Document: *Sub-study 2 Letter of Invitation*) and with a PIS enclosed (Document: *Sub-study 2 Participant Information Sheet*). After approximately a week, a research nurse, or another member of the hospital team, will telephone the woman, answer any questions and, if she wishes to take part, take informed consent (Document: *Sub-study 2 Verbal ICF*).

Option 2: Eligible women who are due to attend a clinic appointment, will be sent (by a research nurse or another member of the hospital team) a letter of invitation signed by her consultant, enclosing a PIS. The woman will be approached about the study at the clinic appointment, any questions she has will be answered, and, if she is willing to take part, informed consent will be obtained (Document: *Sub-study 2 ICF*).

Option 3: Eligible women will be approached and provided with the PIS at a clinic appointment by a research nurse or another member of the hospital team. If not already available, telephone numbers will be obtained for women who are potentially interested in taking part. After approximately a week, a research nurse or another member of the hospital team will telephone the woman, answer any questions and, if she wishes to take part, take informed consent.

Abstraction of clinical details: Relevant clinical details for each woman such as date of diagnosis, stage (T, N, M), grade, date of surgeries, whether they had radiotherapy, whether they had neo-adjuvant AET, date of first AET prescription, and NHS number which is required for linkage, will be abstracted from medical records by the research nurse or another member of the hospital team. It will be made clear on the PIS and consent form that participation in the study involves the

participant agreeing to their medical records being accessed to abstract relevant details and then shared with NHS Digital for the purposes of linkage.

Obtaining prescription encashment data: We will provide a file containing details required for matching (including name, date of birth, NHS number) and the other abstracted clinical details to NHS Digital, which is data controller for the NCRD data, and which can access the PCPD. They will extract records of endocrine therapy and other prescriptions encashed for each woman (e.g. bisphosphonates) during the time from date of breast cancer diagnosis to the date of data extraction and return this information to the research team. NHS Digital will remove personal identifying details and return the pseudonymised linked dataset to the research team for analysis.

The research team will scrutinise this to assess timeliness and likely completeness of AET prescriptions. They will also examine the data on the other prescriptions to determine whether this can be used as part of the health economic assessment of resource use.

If it is not possible to obtain data from NHS Digital, we will seek to obtain GP prescribing data for participants. The focus will be on prescriptions relating to the breast cancer.

G. PARTICIPANT WITHDRAWAL

Participants in either sub-study 1 or sub-study 2 may withdraw from the study at any time with no obligation to provide a reason or explanation. In the event of withdrawal, the participant's personal identifying data will be destroyed but any other data collected (e.g. interview transcript, completed questionnaires, prescribing data) will be retained, as will any screening information that was used to inform their eligibility for the study. Consent forms will be retained but will be marked as a withdrawn participant.

H. END OF STUDY

For sub-study 1, for an individual participant, completion of the follow-up questionnaire or participation in the interview (whichever is the later) will constitute the end of their participation in the study. Overall, the end of the study will be defined as the point when questionnaires and interviews have been completed, all data analysed, and any changes required before the RCT have been made.

For sub-study 2, for an individual participant, providing consent for their hospital records to be linked to the national cancer registry and BSA will constitute the end of their participation in the study. Overall, the end of the study will be defined as the point when the linked data has been obtained and scrutinised for timeliness and completeness.

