	Sub-study 2: Eligible participants will be women diagnosed with early-stage ER-positive invasive breast cancer and prescribed oral AET in the previous 9-36 months with one of the following: (i) T2 and N0, (ii) T1 and N>0, (iii) T2 and N>0 or (iv) T1 and N0 and grade 3 disease.
Planned Size of	Sub-study 1: 45 women with breast cancer, plus 15-18 health professionals
Sample (if	involved in delivering the study at the clinical sites.
applicable)	Sub-study 2: 45 women with breast cancer.
Planned Study	The programme of work will run for 80 months from May 2020.
Period	Workstream 2 will run from months March 2022-June 2023.

C. FUNDING AND SUPPORT IN KIND

FUNDER	FINANCIAL AND NON-FINANCIAL
	SUPPORT GIVEN
National Institute for Health Research (NIHR)	£2,538,229 for the full programme

D. STUDY PROTOCOL: SUPPORTING WOMEN WITH ADHERENCE TO HORMONE THERAPY FOLLOWING BREAST CANCER (SWEET)

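### Sub-study 1: the minimum rate and site number given to support 45 women in three months yield 39; 45 needs about 15 weeks, a higher rate or a fourth site

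*Protocol*

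**What the plan says.** Protocol section 4E sets the sub-study 1 target and its period in one sentence: "We propose to recruit a minimum of 45 eligible women over a period of up to three months". The bracket that follows gives the only accrual basis for it: "anticipating at least one woman per week per site is achievable, and assuming a minimum of 3 sites recruiting". The synopsis gives the same planned size of 45 women.

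Section 4C sets the number of clinical sites for both sub-studies at a "minimum of three NHS clinical sites (this may increase to five if required to support recruitment"). Extra sites are therefore foreseen, but only if recruitment needs them.

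Section 4E also cites an average feasibility study size of 36. It takes the 45 women for sub-study 2 from the reasoning for sub-study 1. The feasibility of recruiting women is an objective in section 3 and the first question in section 4B.

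**The concern.** The sentence in 4E has four parts: a target, a period, a rate and a number of sites. The target is a minimum and the period is an upper limit. For the rate and the site number to justify the target, their planning minimums should deliver at least the minimum target within the maximum period. They do not.

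What is at stake is modest but specific to this study, because recruitment is itself something the study sets out to learn about. If each of three sites recruited exactly one woman per week for three months, the assumed rate would be confirmed and the stated number would be missed. The plan should not lead a reader to two different conclusions from the same result.

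**Working it through.** **Inputs, all from the protocol**

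- Target: at least 45 women (4E; the synopsis gives 45).
- Period: "over a period of up to three months" (4E). Three months is 13 weeks, or 13.04 weeks as a quarter of 365.25 days, or 13.14 weeks as 92 days. Four-week months give 12 weeks.
- Rate: "anticipating at least one woman per week per site is achievable" (4E), so the floor is 1.0 per site-week.
- Sites: "assuming a minimum of 3 sites recruiting" (4E), so the floor is 3. Section 4C allows up to 5.

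**Step 1: can 45 be reproduced?**

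Expected recruits = sites × women per site per week × weeks. At 1.0 per site-week:

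| Weeks | 3 sites | 4 sites | 5 sites |
|---|---|---|---|
| 12 | 36 | 48 | 60 |
| 13 | 39 | 52 | 65 |
| 13.14 (92 days) | 39.4 | 52.6 | 65.7 |
| 14 | 42 | 56 | 70 |
| 15 | 45 | 60 | 75 |

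With three sites, 45 appears only at 15 weeks, which is longer than three months on any reading.

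**Step 2: size of the gap at the floor values**

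- 13 weeks: 45 − 39 = 6 women; 6/45 = 13%.
- 12 weeks: 45 − 36 = 9 women; 9/45 = 20%.

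**Step 3: what would deliver 45**

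- Longer period: 45 / (3 × 1) = 15 weeks, about 3.45 months.
- Higher rate: 45 / (3 × 13) = 1.15 women per site-week, or 45 / 36 = 1.25 over 12 weeks.
- Fourth site: 4 × 13 = 52 women in 13 weeks, with 45 reached at 45/4 = 11.25 weeks.

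**Step 4: chance variation**

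Assume, beyond what the protocol states, that recruitment is Poisson at exactly 1.0 per site-week with every counted site open throughout.

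- 3 sites, 13 weeks: P(X ≥ 45 | mean 39) = 0.187.
- 3 sites, 12 weeks: P(X ≥ 45 | mean 36) = 0.082.
- 3 sites, 15 weeks: P(X ≥ 45 | mean 45) = about 0.52.
- 4 sites, 13 weeks: P(X ≥ 45 | mean 52) = 0.852.

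These figures use a stated lower bound as the mean, so they describe the floor case only.

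**The case against.** The strongest reply is that the rate and the site number are floors. The text says at least one woman per week and at least three sites, so 39 is the yield at the floor and not a ceiling. Forty-five is compatible with the protocol at a rate only 15% higher, or with one more site. This stands, and it rules out the reading that the plan can recruit only 39. It does not remove the mismatch, because 45 is also called a minimum, three months is a maximum, and no higher expected rate is given anywhere.

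Several stronger consequences might be inferred, and the protocol does not support them:

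- **That missing 45 by month three would count as failed feasibility.** No progression criterion or pass/fail rule is tied to that number. The recruitment question in 4B is open, and screening logs, reasons for declining and interviews with patients and staff all inform it.
- **That sites would have to be opened outside the plan.** Section 4C provides for it: "this may increase to five if required to support recruitment".
- **That the main trial's recruitment forecast rests on the same error.** This protocol covers Workstream 2 only and contains no such forecast.
- **That the figure depends on all three sites opening on day one.** The protocol does not say so. In section 4F the staff interviews are timed from three months of recruitment at each site. On a per-site clock, staggered opening loses no site-weeks, and the floor yield is still 39.

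The practical effect is also small. Thirty-nine women would exceed the cited average of 36 and would cover the 20 to 30 patient interviews planned in section 4F. Workstream 2 runs from March 2022 to June 2023, so two further weeks are short against the whole, although 4F does describe the timetable as tight.

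**Conclusion.** The point holds as a minor correction to a stated planning figure. The planning minimums in 4E give 39 women in 13 weeks (36 in 12) against a stated minimum of 45, a shortfall of 6 (13%). No reading of three months closes the gap at three sites and one woman per week.

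The arithmetic rests only on the protocol's own inputs. The 19% figure rests in addition on Poisson accrual at exactly the floor rate with three sites open for 13 weeks. A reader might take it as the probability that the study succeeds in recruiting. It is not, because the protocol allows both a faster rate and more sites.

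Sub-study 1 is single-arm with no hypothesis test, so no power or error rate changes.

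**What to change.** Make the target, period, rate and site number in section 4E agree. The simplest change is to restate the recruitment period as up to about 15 weeks at three sites. It costs about two more weeks. At the floor rate it makes 45 the expected number, with only about a 52% Poisson chance of reaching it.

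The alternative is to keep three months and state what that requires. One option is a rate of about 1.15 women per site per week, with the reason for expecting it. The other is a fourth site from the start, which raises the floor-rate expectation to 52 and the chance of reaching 45 to about 85%, at the cost of setting up one more site.

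Under either choice, report recruitment as women per open site-week against the assumed 1.0. This answers the recruitment question however many sites open and whenever they do. Leaving this measure out of the protocol is not an error, and it may be in an analysis plan that is not shown. Each site's opening date has to be recorded for it. Otherwise the change is to protocol wording only. Section 4E should also say whether the accrual reasoning is meant to carry over to the 45 women in sub-study 2.
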